The online baseline assessment includes valid measures of hookah and other tobacco use behavior, hookah beliefs, perceptions, and other constructs from our conceptual framework. After completing a baseline, participants will be randomly assigned in approximately equal numbers to one of two arms: 1) hookah tobacco education messaging; 2) control arm. Randomization will be balanced by hookah use status (susceptible non-user, current user) to ensure sufficient numbers of these characteristics across study arms. Participants in the hookah education messaging arm will then receive 4 study communications delivered approximately weekly during the exposure period. These communications will consist of: 1) the study hookah education messages; and 2) brief post-message (approximately 5 minutes) measures of hookah use behaviors, beliefs and perceptions, and message responses. Procedures for participants randomized to the control arm will be similar, however communications will consist of non-tobacco messages communicating about sun protection that we have developed on our previous work and pilot tested against tobacco-related messaging to ensure they are an adequate contact-matched control. Messages will have a similar layout and structure (e.g., amount of text) to the hookah public education messages and will be presented in a consistent order for all participants. We chose this contact-matched control arm to ensure groups are treated equivalently with only message content varying between arms.

PROTOCOL TITLE: Randomized Trial Testing the Efficacy of Hookah Tobacco Public Education Messages among Young Adults

All participants will complete follow-up assessments online 2-, 4-, and 6-months after the message exposure period. We chose these time points based on our team's prior work on young adult tobacco use behavior and messaging,^{44, 45} other research on hookah tobacco messaging,²¹ recommendations for follow-up in tobacco intervention research,^{47, 48} and because this follow-up frequency and duration will capture short term message effects and changes in hookah use, susceptibility, and mediating processes.^{12, 14, 21, 47, 49-52} As with the baseline, follow-ups will be securely administered online. Measures are attached in Section 14. At the conclusion of the final follow-up, all participants will be debriefed on the study goals and the potential risk of hookah and other forms of tobacco use.

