17.0 Data Management* and Confidentiality

17.1 We calculated statistical power to test our study hypotheses assuming a two tailed $\alpha = .05$ and baseline sample of 1100 participants, including 425 young adult hookah users and 675 susceptible non-users. We estimated the ability to detect effects of the messages on hookah initiation among susceptible non-users⁴⁴ and cessation among current users²¹ based on prior studies. Among susceptible non-users, we estimate 8% will initiate hookah use over the 6-month follow-up period based on our recent national study of US young adults.⁴⁴ With susceptible non-users at 6-month follow-up we will have 80% power to detect percent differences as small as 5.3%, or initiation of 8% in the control arm and 2.7% in the messaging arm. This equates to an odds ratio of 0.62 comparing hookah initiation between the messaging and control arms in a logistic regression analysis including covariates. Although evidence on hookah tobacco cessation rates is limited, 1 prior study found that young adult hookah users exposed to risk-based messages were nearly 2 times more likely than those in a control condition with no message exposure to report cessation at 6-month follow-up (62% vs. 33%, odds ratio 1.89).²¹ Conservatively assuming a much lower overall cessation rate of approximately 10% (i.e., comparable to those of behavioral smoking cessation interventions)⁵³ the sample of hookah users at the 6-month follow-up will have 80% power to detect absolute differences in cessation between study arms as small as 8% (10% control, 18% messaging). In a logistic regression analytic framework with covariates, this equates to an odds ratio of 1.55. For analyses of continuous outcome variables, our sample will provide 80% power to detect small mean differences ($d \leq 0.10$) between arms in the complete sample, and among susceptible non-users and current users separately. For testing mediating effects,

PROTOCOL TITLE: Randomized Trial Testing the Efficacy of Hookah Tobacco Public Education Messages among Young Adults

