simulation studies provide estimated power to detect mediation effects using bias-corrected bootstrap analyses.⁵⁴ The sample will provide 80% power to detect small- to medium- indirect (i.e., coefficients in the range of 0.20-0.30) effects. Similarly, for analyses of the interaction between study condition and two-level moderators we will have 80% power to detect moderator effects as small as Cohen's $f \leq 0.10$ in ANCOVA analyses (i.e., differences between susceptible non-users and hookah users) and odds ratios as small as 1.70 for interactions between non-hookah tobacco use and trial arm for binary initiation and cessation outcomes.

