We will test hypotheses about potential mediation of message effects through a series of steps drawing from traditional mediation frameworks for preliminary analyses⁵⁷ and applying more robust methods to formally test for mediation.⁵⁸ First, we will examine differences in means for mediating variables by trial arms and investigate whether each mediator at 1- and 3-month time points is correlated with the outcomes at 6-months using bivariate statistics and regression-based analysis accounting for any covariates as needed. Where these preliminary steps indicate potential mediation, we will formally test for mediation by estimating the indirect effects of candidate mediators at 1- and 3-months on study outcomes at 6-

PROTOCOL TITLE: Randomized Trial Testing the Efficacy of Hookah Tobacco Public Education Messages among Young Adults

months via the study arms using a bias-corrected bootstrapping method with 1,000 resamples to address non-normality of the product of the coefficients estimator.^{54, 58} This bootstrapping approach estimates an indirect (i.e., mediation) effect reflecting the product of the effect of trial arm on the mediator with the effect of the mediator on the outcome, and produces bias-corrected asymmetric 95% confidence intervals (CIs) that correct for non-normality of the distribution of indirect effects.⁵⁸ This method provides higher power and better control over the Type I error rate compared with traditional approaches for testing mediation.^{172,173} Asymmetric 95% CIs for indirect effects that do not include zero will indicate significant mediation effects.¹⁷² We will evaluate hypothesized moderators individually by introducing them one at a time and their corresponding interactions with trial arm into the logistic regression and ANCOVA models. Analyses assessing differential effects of messages among susceptible non-users and hookah users will primarily be ANCOVA based and examine mediators and outcomes measured commonly in these groups. Although the primary moderators of interest are those relating to hookah and other tobacco product use, we will also explore potential moderating effects of participant demographics including sex (male, female) and age (< 25, 25+) and other characteristics in analyses.

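### The other-tobacco moderator test on initiation splits only 6 to 9 expected messaging-arm events, and no method is prespecified for a cell with none

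*Combined protocol and SAP*

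**What the plan says.** Hypothesis 2b (section 2.2) predicts larger message effects in people who do not use other tobacco products than in those who do. In section 17.1 moderators are entered one at a time, with "their corresponding interactions with trial arm into the logistic regression and ANCOVA models". The same section ranks other tobacco use among the main moderators and claims 80% power for odds ratios as small as 1.70 "for interactions between non-hookah tobacco use and trial arm for binary initiation and cessation outcomes".

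The sample is 1,100, "including 425 young adult hookah users and 675 susceptible non-users". The design contrast for initiation at 6 months is "initiation of 8% in the control arm and 2.7% in the messaging arm", for which 80% power is claimed. The same passage equates this contrast with an odds ratio of 0.62.

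Section 6.2 balances randomisation by hookah use status, not by other tobacco use. It gives no retention target for this trial and cites only similar studies that kept 70% or more. Nowhere do the documents give the share of susceptible non-users who use other tobacco, initiation rates by other tobacco use, a minimum event count, or an exact, penalised or other method for sparse cells.

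**The concern.** With arm, a binary moderator and their product, the logistic model has one free parameter for each of the four cells. If a cell has no initiations, its fitted log-odds goes to minus infinity and takes the interaction with it. Software then reports non-convergence or a very large coefficient with a huge standard error, and the Wald interval and p-value cannot be used. Adding covariates does not restore the missing information.

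The initiation part of Hypothesis 2b is exposed to this because the events are few and the plan splits them again. If it happened, the analyst would have to choose a remedy after seeing the data, for a hypothesis that the protocol names in advance.

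**Working it through.** **Inputs from the documents.** 675 susceptible non-users, allocated 1:1, so 337.5 per arm; initiation 8% (control) and 2.7% (messaging). Retention is varied from 70% (the cited precedent) to 100%.

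**Assumptions not in the documents.** The share *s* of susceptible non-users who use other tobacco is taken as 25%, with a range of 15% to 50%. Risk is first taken as equal in both moderator levels.

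**The plan's main-effect figure.** Detecting 8% versus 2.7% with 80% power at two-sided 0.05 needs 282 per arm, or 564 in total, which is 564/675 = 83.6% retention. Power is 78.3% at 80% retention and 72.7% at 70%. The design rates therefore fit retention of about 84%, which is included below.

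**Events in the messaging arm.** Number per arm × 0.027:
- 100% retention: 337.5 × 0.027 = 9.1
- 84%: 283.5 × 0.027 = 7.7
- 70%: 236.25 × 0.027 = 6.4

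**Smallest cell at *s* = 25%** (other-tobacco users, messaging arm). Expected events are n × 0.25 × 0.027, and the chance of none is 0.973 raised to the cell size. The chance that any of the four cells is empty is 1 − ∏[1 − (1 − p)^n].

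| Retention | Cell size | Expected events | P(this cell empty) | P(any cell empty) |
|---|---|---|---|---|
| 100% | 84.4 | 2.3 | 9.9% | 10% |
| 84% | 70.9 | 1.9 | 14.4% | 15% |
| 70% | 59.1 | 1.6 | 19.9% | 21% |

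**Other shares, same formula.** P(any cell empty) at 100% and at 70% retention: 26% and 41% at a 15% share; 16% and 29% at 20%; 6% and 16% at 30%; 4% and 12% at 35%; 2% and 8% at 50%.

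**Other risk patterns at *s* = 25%,** at 100%, 84% and 70% retention:
- Messaging rate 5.1%. The odds are 0.62 × 0.08/0.92 = 0.0539, so the risk is 0.0539/1.0539 = 5.1%. Result: 1%, 3%, 5%.
- Other-tobacco users have twice the odds of initiating in both arms, overall rates kept: 3%, 5%, 10%.
- Hypothesis 2b true at the stated interaction odds ratio of 1.70, overall 2.7% kept. Messaging-arm risks are then 3.9% in users and 2.3% in non-users. Result: 4%, 7%, 12%.
- No message effect (8% in both arms): 1.5% or less.

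**Cessation** (425 users, 10% versus 18%): about 1% or less at a 30% share.

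**Does a penalised fit cure it?** In this four-cell model Firth's method amounts to adding one half to the events and non-events of each cell. Take a 70%-retention example: 0/59 and 5/177 initiations in the messaging arm (other-tobacco users, non-users), 5/59 and 14/177 in control. Maximum likelihood is infinite. Firth gives [ln(0.5/59.5) − ln(5.5/54.5)] − [ln(5.5/172.5) − ln(14.5/163.5)] = −2.49 + 1.02 = −1.46, an odds ratio of 0.23. In 600 simulated trials with 472 followed up and no true interaction, ordinary logistic regression gave an absolute log interaction odds ratio above 5 in 24%. Firth's estimate was finite in all, with a largest value of 3.1 and a mean near zero.

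**Precision remains poor.** The variance of the log interaction odds ratio is the sum of 1/[n p (1 − p)] over the four cells. At a 30% share and 70% retention the standard error is 1.02, and two-sided power for an odds ratio of 1.70 is 7.5%. At a 50% share and full retention they are 0.78 and 10%.

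**The case against.** The strongest reply is that the 10% to 21% depends on three inputs the documents do not settle: the moderator share, the 2.7% rate and equal risk across levels. The share is not given at all. The 2.7% is a detectable alternative rather than a forecast, and the odds ratio of 0.62 stated beside it implies about 5.1%. Hypothesis 2b itself predicts more messaging-arm events among other-tobacco users than equal risk allows. All of this stands. It is why the result is conditional and why the 1% to 12% range is given beside it.

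Two stronger readings are tempting. A reader might infer that the main initiation model needs the same treatment. It does not: the chance of no messaging-arm events at all is 0.973^236 = 0.16% at 70% retention and 0.01% with nobody lost. A reader might also infer that covariates should be capped at some number. No calculation here supports a particular cap.

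It is also fair that a likelihood-ratio test and a one-sided profile interval survive an empty cell, and that the plan does not commit to Wald inference. But it names no alternative either. Finally, section 17.1 starts from mixed-effects logistic regression, whereas standard Firth software fits fixed effects. That is a real cost, though confined to one model with one 6-month outcome per person.

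**Conclusion.** The point holds as a conditional one. It is firm that 6 to 9 expected messaging-arm initiations at the design rates are to be divided by a prespecified moderator, that an empty cell makes the maximum-likelihood interaction infinite, and that no method is named for that case.

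The frequency is less firm. It is about 10% to 21% at a 25% share with equal risk and 100% to 70% retention, and about 2% to 41% over shares of 15% to 50%. At a 25% share it falls to about 1% to 12% if the messaging rate is 5.1%, if other-tobacco users have twice the odds of initiating, or if Hypothesis 2b is true at an odds ratio of 1.70. The documents do not support an unconditional failure rate. Nor do they support the view that all of Hypothesis 2b is at risk: the cessation and ANCOVA strands are not materially affected.

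This is an inexpensive improvement to one analysis. It is separate from the power statement for the same interaction, which cannot be reproduced and which a penalised fit does not repair.

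**What to change.** In the moderation paragraph of section 17.1, state that the arm-by-moderator models of 6-month initiation will use Firth penalised-likelihood logistic regression, with profile-likelihood confidence intervals and penalised likelihood-ratio tests, fitted as a fixed-effects model to the single 6-month outcome. Leave the main initiation model, the cessation models and the ANCOVA models as planned. Report the number of initiations in each arm-by-moderator cell beside the estimate.

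The cost is slight shrinkage of the odds ratio towards 1, slightly biased predicted risks, and no random effect in this one model. No extra participants or data are needed. Correct the claim of 80% power at an interaction odds ratio of 1.70 separately, and present the initiation interaction as an imprecise estimate.

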AmeriSpeak panel members who are young adults ages 18 to 30 in the US will be sent a standard email invitation describing the study. Potential participants are identified by randomly selecting households within the panel with a young adult within the study age range, and targeting study invitations based on recent study participation, and other demographic characteristics as needed to ensure a representative sample. This email invitation will introduce study procedures and eligibility criteria, and direct interested panel members to the eligibility screener with items to confirm eligibility. Procedures will ensure potential participants are adults ages 18 and older through two steps: 1) targeting study invitations only to those panel members whose age is within this range; and 2) re-assessing age at eligibility screening and excluding those who provide inconsistent information (i.e., ages differ in self-reported screening compared with panel-based age derived from date of birth). Panel members who are confirmed to meet study eligibility criteria will proceed to the online baseline. AmeriSpeak panel members who do not meet study eligibility criteria will be redirected to a concluding thank-you screen. Similar procedures will be followed when participants are contacted for the brief message exposures and the 2-, 4-, and 6-month follow-up assessments. This approach is guided by similar previous tobacco research studies with young adults, including studies with prospective participation and retention rates of 70% and higher.⁴⁵⁻⁴⁶

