10.0 Inclusion and Exclusion Criteria*

10.1 NORC AmeriSpeak panel members will be recruited and screened for eligibility through a series of steps. NORC will send an email invitation using their standard template to potential participants and will introduce study procedures and eligibility criteria to AmeriSpeak panel members. Interested panel members will be directed to the online eligibility screener with valid self-report items to confirm eligibility. Invitations will be targeted by NORC using data from the member panel enrollment profile (i.e., participant age) and confirmed based on responses to the brief online eligibility screener.

10.2 Eligible participants for the randomized trial will be 1) young adults ages 18 to 30; 2) who have never used hookah tobacco but are deemed susceptible based on 4 screening questions or report hookah tobacco use at least once within the past month based on valid measures;²³ ²⁴ and 3) are NORC AmeriSpeak panel members residing in the US.

Study exclusion criteria include: 1) individuals who are younger than 18 or over 30 years of age; 2) those who do not meet self-report criteria for susceptibility or current use of hookah tobacco; or 3) are not registered to participate in research studies through the NORC AmeriSpeak panel.

10.3 Study participants will be Amerispeak panel members who meet the eligibility criteria listed above. The following special populations will be excluded: Adults who are unable to consent, individuals who are not yet adults, pregnant women, and prisoners.

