17.2 NORC also takes extensive measures to ensure that all panel members' privacy and personal information are treated confidentially and kept secure. All personally identifying records are kept secured in a separate data servers maintained by NORC. NORC never provides any panel members' personally identifying information to a research partner without the explicit and informed consent provided by the sampled members. For this study, all data will be de-identified and anonymous to the investigators and no personal information will be released to the investigators, therefore there will be no way to discern participants' identities from the study data. All NORC survey response data are identified only by an anonymous ID number.

17.3 In addition to the measures put into place by NORC, our research team will take several additional steps to ensure data collected from AmeriSpeak panel members are treated as secure and confidential at GUMC. First, as noted above, all data will be anonymous and will not include personally identifying information. Any data to be transferred from NORC to [name] at GUMC/LCCC will use Georgetown Box. We will use Georgetown Box to transfer data files and documentation to [name] by creating a restricted access link that is password protected and only accessible to authorized NORC personnel. Second, once study data are transferred to GUMC/LCCC all electronic study data files will be securely stored on a GUMC/LCCC network drive. This network space is encrypted and directories are password-protected at the individual user level to ensure electronic data files are treated as secure and confidential. Only the GUMC/LCCC Principal Investigator and authorized study

PROTOCOL TITLE: Randomized Trial Testing the Efficacy of Hookah Tobacco Public Education Messages among Young Adults

personnel will be granted access to the data after appropriate permissions are established.

17.4 All study procedures use well-validated assessments with established psychometric properties. Quality control will be ensured by working with NORC to review online assessments we provide to ensure they function properly in terms of item performance, skip logic, and design. There are no other necessary quality control measures.

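### The exploratory age moderator is cut at 25 although exact age is held; if the message effect changes roughly linearly with age, the cut loses about 25% to 35% of the information on the arm-by-age interaction for evenly spread or bell-shaped ages

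*Combined protocol and SAP*

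**What the plan says.** Section 17.1 tests moderators by "introducing them one at a time and their corresponding interactions with trial arm into the logistic regression and ANCOVA models". The main moderators are hookah use and other tobacco use, in line with Hypothesis 2b in Section 2.2. Demographics come second: "we will also explore potential moderating effects of participant demographics", listed as "sex (male, female) and age (< 25, 25" with the upper group open-ended (25 and over). The section gives no reason for the cut at 25 and plans no analysis of age in years.

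Eligibility in Section 10.2 covers "young adults ages 18 to 30", which is 13 whole years of age. Section 6.2 shows that exact age exists for those screened, because people are excluded when "ages differ in self-reported screening compared with panel-based age derived from date of birth". Section 17.2 says that "no personal information will be released to the investigators". Neither it nor Section 17.3, on data transfer, says whether age in years is in the file sent to the investigators.

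**The concern.** A single cut treats participants aged 18 and 24 as alike and those aged 24 and 25 as different. If the message effect rises or falls gradually over 18 to 30, the two-group contrast uses only part of the variation in age. A real gradient is then easier to miss, and one that is found would be reported as a step at 25. What is at stake is an exploratory description of how message effects vary with age within the eligible range. The trial's main conclusions do not depend on it.

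**Working it through.** **Inputs from the plan.** Age range 18 to 30 (Section 10.2); cut at 25 and arm-by-moderator interaction (Section 17.1); two-sided 5% level and baseline sample of 1,100, made up of 425 users and 675 susceptible non-users (Section 17.1); equal allocation (Section 6.1); retention of 70% or more in similar studies (Section 6.2); mean ages of 24.1, 25.3, 25.3 and 24.8 in earlier samples (Section 3.2).

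**Assumptions.** The documents give neither the trial's age distribution nor the shape of any age effect. The base case is a linear change in effect with age and equally frequent whole years. Other age shapes are shown below.

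**Step 1: the plan's own figure.** No power is stated for age. The nearest statement is 80% power for two-level moderators at Cohen's f of 0.10 in ANCOVA. With a noncentral F test on 1 and N − 4 degrees of freedom and noncentrality N × f²:
- N = 770 (70% of 1,100): noncentrality 7.7, power 79.1%
- N = 785: power 79.9%
- N = 1,100: noncentrality 11.0, power 91.2%

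The stated 80% is therefore reproduced at about 70% retention.

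**Step 2: information kept by the cut.** Under randomisation, age is independent of arm. For an interaction linear in age, the efficiency of the cut relative to age in years is the squared correlation between age and the indicator of being 25 or over:

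efficiency = p(1 − p)(mean age at 25+ − mean age under 25)² / Var(age)

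For equally frequent whole years 18 to 30:
- p = 6/13 and 1 − p = 7/13
- group means 27.5 and 21, difference 6.5
- Var(age) = (13² − 1)/12 = 14
- efficiency = (6/13)(7/13)(6.5²)/14 = 0.2485 × 42.25/14 = 0.750

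**Step 3: effect on power.** If age in years gives 80% power, the standardised effect is 1.96 + 0.84 = 2.80. With the cut, power = Φ(2.80 × √0.75 − 1.96) = Φ(0.465) = 0.68. A simulation (1,100 participants, 4,000 runs, normal outcome, linear interaction) gave 80.3% with age in years and 66.8% with the cut.

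**Step 4: other age distributions, still with a linear change.**

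| Assumed ages, 18 to 30 | Information kept | Lost |
|---|---|---|
| Equal whole years | 75% | 25% |
| Continuous uniform, 18 to under 31 | 74.6% | 25.4% |
| Truncated normal, centre 24 to 25.3, SD parameter 2.5 to 6 | 65% to 73% | 27% to 35% |
| Monotone skewed | 66% to 75% | 25% to 34% |
| Mild to moderate U shape | 79% to 85% | 15% to 21% |
| Only ages 18–20 and 28–30 | 97% | 3% |

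The centres in the third row cover the mean ages reported in Section 3.2. The SD range is an assumption, since no age SD is given. At 65% and 73% kept, the Step 3 formula gives power of about 62% and 67%.

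**Step 5: the opposite case.** If the effect truly steps at 25, the same simulation gives 80.2% power with the cut and 68.3% with a linear age term.

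**The case against.** The strongest reply is that the figure depends on a shape the documents do not give. Step 5 shows that a linear term loses about as much under a true step as the cut loses under a linear gradient. The cut is also prespecified and fits the plan's two-level moderator framework. This stands as a limit on the claim: the loss is conditional, and a linear term alone is not better in every case. It does not justify testing only the cut, because the plan offers no reason to expect a step at 25.

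Three stronger readings are tempting, and the documents do not support them.

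- *The interaction test is already short of power.* This is not shown. No power is stated for age, and the one ANCOVA figure for two-level moderators is reproduced at 70% retention. The fall from 80% to 68% illustrates the ratio; it is not an estimate of this trial's power.
- *The cut weakens a central test of who benefits.* Hypothesis 2b names hookah use status and other tobacco use. Age is exploratory, and no hypothesis, endpoint or power statement rests on it.
- *Exact age is already in the investigators' hands, so the change is free.* Section 6.2 shows only that the panel operator holds it. Whether age in years is transferred is not stated.

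**Conclusion.** The point holds in conditional form and is minor. Given a roughly linear change in effect with age, testing age only as under 25 versus 25 and over keeps about 75% of the interaction information for equally frequent ages, and about 65% to 73% for bell-shaped ages centred on the pilot means. The loss is smaller for U-shaped ages and absent for a true step at 25. The ratio is the result to carry forward. Translating it to 825 of 1,100 people (0.75 × 1,100) describes the full baseline sample only, since initiation and cessation are analysed separately in the non-user and user groups and with fewer people at six months. The primary comparisons and the hypothesised moderators are untouched.

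**What to change.** In Section 17.1, state that the arm-by-age interaction will be tested with age in whole years as a continuous term, with one prespecified check of shape (a quadratic term or a spline with few degrees of freedom). Keep the under 25 and 25-and-over results for description only. Confirm with the panel operator that the de-identified file includes age in whole years.

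The cost is a change of wording and that one confirmation. No new data, sample size change or participant burden is involved. The downside is lower power from the linear term if the effect is a step at 25. The shape check covers this only in part and adds at least one parameter to an exploratory test.
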